### **2.2.4.2. Functional Health Status**

Changes from baseline in the Pediatric Data Outcomes Collection Instrument (PODCI) score as compared to placebo by Week 17, 33 and 49. Within subject change from baseline in the PODCI through Week 97. See [Appendix 3](#).

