### **3.2. Duration of Subject Participation**

Subjects' participation will begin during the screening period (up to 6 weeks) followed by two dosing periods (48 weeks each) and 2 final study visits (ending 12 weeks after the last study dose). Subjects, who are enrolling in the OLE study, will only be required to return for 1 final study visit at Week 97. Subjects will return to the site monthly for study drug administration (24 visits) as well as completion of safety and efficacy assessments.

For the first 12 subjects enrolled who are undergoing the additional PK testing, a total of 34 visits are required. The remaining subjects will be expected to attend 28 visits. The total time on study for all subjects will be approximately 105 weeks (26 months including screening).

In order to assure consistency in assessment collection, visits that include functional assessments and imaging assessments (DXA and thigh MRI) will be collected over a 2-day period within the study visit window. In the case where subjects are traveling from a distance, the site will offer nearby overnight accommodations.

Per the local requirements in Japan, all Japanese subjects will be hospitalized for an overnight observation following the first and second treatment (Day 1 and 29).

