#### 4.1. Inclusion Criteria

Subject eligibility should be reviewed and documented by an appropriate member of the investigator's study team before subjects are included in the study.

Subjects must meet all of the following inclusion criteria to be eligible for enrollment into the study:

1. Ambulatory boys age 6 to <16 years old (at the time of randomization), diagnosed with DMD. Diagnosis must be confirmed in subject's medical history and by genetic testing obtained during routine clinical care for diagnostic purposes as reported from an appropriate regulated laboratory using a clinically validated genetic test (genetic testing is not provided by the sponsor). Results must confirm the presence of a mutation in the dystrophin gene(s) which is clinically consistent with the diagnosis of DMD.
2. Subjects who are able to perform the 4 stair climb in  $\geq 0.33$  but  $\leq 1.6$  stairs/second at screening.\*
3. Evidence of a personally signed and dated informed consent and assent (where appropriate) document indicating that the subject and a legally acceptable representative/parent(s)/legal guardian have been informed of all pertinent aspects of the study.
4. Subjects and their legal guardians who are willing and able to comply with scheduled visits, treatment plan, laboratory tests, and other study procedures. Subjects will be required to provide assent in compliance with local regulations and IRB requirements.
5. Subjects must be receiving glucocorticosteroids for a minimum of 6 months prior to signing informed consent. There should be no significant change ( $>0.2$  mg/kg) in dosage or dose regimen (not related to body weight change) for at least 3 months immediately prior to signing the informed consent and a reasonable expectation that dosage and dosing regimen will not change significantly for the duration of the study.
6. Adequate hepatic and renal function on screening laboratory assessments:
  - $\text{GGT} \leq$  upper limit of normal (ULN).
  - Alkaline phosphatase  $\leq$  ULN.
  - Total Bilirubin  $\leq$  ULN.
  - Serum Albumin  $\geq$  LLN.
  - Serum creatinine  $\leq$  ULN.
7. No underlying disposition for iron accumulation on screening laboratory assessments:

- Serum Iron  $\leq 1.2 \times$  ULN.
  - Serum Ferritin  $\leq 140$  ng/mL.
  - % Transferrin Saturation  $\leq 50\%$ .
8. No underlying disposition for bleeding disorder on screening laboratory assessments:
- PT/INR  $\leq 1.25 \times$  ULN.
  - aPTT  $\leq 1.25 \times$  ULN.

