#### **4.5. Caregiver(s)**

The parent or legal guardian of the subject will actively participate as caregiver in this study. As caregiver, the parent or legal guardian will not only provide informed consent, but will also actively participate in the study procedures including completing the PODCI questionnaire and being interviewed for the C-SSRS on behalf of the subject. They will be responsible for collection of the fecal sample and providing feedback during the wellness calls. The caregiver will communicate observed safety information to the Investigator or designee as appropriate. The investigational site will train the caregiver on instructions to collect and/or ship a fecal sample, as needed, and provide other instructions on preparing the subject for each study visit.

A subject's caregiver(s) must meet all of the following criteria for the subject to be eligible for enrollment in the study:

- Is  $\geq 18$  years of age and has demonstrated responsibility as a caregiver through monitoring the subject and reporting any observed AEs.
- Is available to accompany the subject to the clinic visits.
- Can follow instructions.
- Is willing and able to give written informed consent.

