### **6.9. Visits 33 (Follow-up Day 673)**

A two day visit will be required to complete assessments at this visit. MRI-thigh and functional assessments should be collected on separate days. Functional assessments should routinely be collected in the morning when the subject is rested and well fed. The MRI-thigh should routinely be collected at approximately the same time of day throughout the study.

- **Fecal occult blood:** Fecal sample is to be collected at home within approximately 1 week prior to scheduled visit.
- **C-SSRS:** Children's Since Last Visit (Version 6/23/10).
- **PODCI** questionnaire.

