### **7.11. Pediatric Outcomes Data Collection Instrument (PODCI)**

In order to evaluate subject's functional health status, the PODCI questionnaire will be collected. The PODCI is a patient-reported assessment of musculoskeletal health intended for use in children and adolescents. The pediatric version intended for completion by parents or caregivers of children aged 10 years or younger will be utilized in this study. The instrument is organized into multiple domains: upper extremity function, transfers and mobility, physical function and sports, comfort (pain free), happiness and satisfaction, and expectations for treatment. Each domain produces an independent score, and a summary total score is also computed. Scores may be reported as standardized, or they may be converted to normative scores based on the scores reported in a large, healthy population.

The PODCI will be collected electronically on a tablet device.

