## Outcomes Questionnaire

*Developed by:*

American Academy of Orthopaedic Surgeons®

Pediatric Orthopaedic Society of North America

American Academy of Pediatrics

Shriner's Hospitals

To be completed by the parent for children 2 – 10 years old

*Based on the Version 2.0 Pediatrics-Parent/Child Outcomes Instrument*

*Also commonly referred to as the PODCI ("Pediatric Outcomes Data Collection Instrument")*

*Revised, renumbered, reformatted August 2005*

Today's Date     /     /

Thank you for completing this questionnaire!

This questionnaire will help us to better understand your general health and any problems related to bone and muscle conditions.

Your completion of this questionnaire is completely voluntary and your responses will be held in the strictest confidence.

Please answer every question. Some questions may look like others, but each one is different.

There are no right or wrong answers. If you are not sure how to answer a question, just give the best answer you can. You can make comments in the margin. We do read all your comments, so feel free to make as many as you wish.

Your Child's Birth Date     /     /

Your Child's Social Security Number \_\_\_\_\_

Your Social Security Number \_\_\_\_\_

090177e1909dc770\Approved\Approved On: 25-Mar-2019 05:50 (GMT)

Some kind of problems can make it hard to do many activities, such as eating, bathing, school work, and playing with friends. We would like to find out how your child is doing. (Circle one response on each line.)

During the **last week** was it easy or hard for your child to:

	Easy	A little hard	Very hard	Can't do at all	Too young for this activity
1. Lift heavy books?	1	2	3	4	5
2. Pour a half gallon of milk?	1	2	3	4	5
3. Open a jar that has been opened before?	1	2	3	4	5
4. Use a fork and spoon?	1	2	3	4	5
5. Comb his/her hair?	1	2	3	4	5
6. Button buttons?	1	2	3	4	5
7. Put on his/her coat?	1	2	3	4	5
8. Write with a pencil?	1	2	3	4	5

9. On average, **over the last 12 months**, how often did your child miss school (preschool, day care, camp, etc.) because of his/her health?

1. Rarely
2. Once a month
3. Two or three times a month
4. Once a week
5. More than once a week
6. Does not attend school, etc.

During the **last week** how happy has your child been with: (Circle one response on each line.)

	Very happy	Somewhat happy	Not sure	Somewhat unhappy	Very unhappy	Child is too young
10. How he/she looks?	1	2	3	4	5	6
11. His/her body?	1	2	3	4	5	6

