### 3.3.3. Exploratory Endpoints

- *Changes from baseline in the Pediatric Data Outcomes Collection Instrument (PODCI) score as compared to placebo by Week 17, 33, and 49. Within subject change from baseline in the PODCI through Week 97.* The last pre-dose value will serve as the baseline for the PODCI questionnaire. The results will be presented by the Global Function score and the five domains: Upper Extremity and Physical Function; Transfer and Basic Mobility; Sports and Physical Functioning; Pain/Comfort and Happiness.

090177e1909dd632\Approved\Approved On: 25-Mar-2019 05:54 (GMT)

- *Mean percent change from baseline as compared to placebo in lean body mass by whole body DXA by Week 17, 33, and 49. Within subject from baseline in lean body mass through Week 97.*
- *Changes from baseline in muscle quality and fat fraction as compared to placebo as measured by T2-mapping and Dixon MRI Week 17, 33, and 49. Within subject change from baseline in T2-mapping and Dixon MRI at Week 97. Depending on the imaging capabilities at each site, this data may only be collected at a subset of sites.*

Specifically, these thigh MRI endpoints will include

- Whole Thigh Mean Fat Fraction, as measured by Dixon MRI, which is the mean fat fraction for the entire thigh muscle bundle (ie, muscle and inter/intra-muscular fat regions)
- Mean T2 relaxation time, which is the mean T2 value across the muscle bundle in a section of the thigh; and
- Percent Probable Muscle and Percent Probable Fat (ie, 100% - Percent Probable Muscle), which are derived from the T2 mapping acquisition.

Details of the thigh MRI measures are provided in the Study Imaging Review Charter.

- *Quantification of changes as measured by blood biomarkers (pharmacogenomic and liver).*
- *In subjects randomized to Sequences 1 and 2, duration of treatment response will be evaluated within subjects as compared to baseline for all efficacy (function and strength), pharmacologic and PD endpoints previously described through Week 97.*
- *In subjects randomized to Sequence 3, treatment response will be evaluated within subjects as compared to baseline for all efficacy (function and strength), pharmacologic and PD endpoints previously described through Week 97.*

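### The only PODCI form is the parent version for ages 2-10, so assessments of boys aged 11 or older fall outside its stated range

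*Protocol*

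**What the plan says.** Eligibility, Protocol Section 4.1, criterion 1: "Ambulatory boys age 6 to <16 years old (at the time of randomization), diagnosed with DMD".

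Instrument, Protocol Section 7.11: "The pediatric version intended for completion by parents or caregivers of children aged 10 years or younger will be utilized in this study". Appendix 3 reproduces that form and no other; its cover reads "To be completed by the parent for children 2 – 10 years old". Under Section 4.5 the parent or guardian "will also actively participate in the study procedures including completing the PODCI questionnaire", with no distinction by the boy's age.

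Schedule: PODCI is given at screening and baseline, then repeatedly to Visit 33 (Week 97, Day 673) or early withdrawal (Schedule of Activities; Sections 6.1, 6.2, 6.6, 6.8, 6.9 and 6.12).

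Endpoint, SAP Section 3.3.3: "Changes from baseline in the Pediatric Data Outcomes Collection Instrument (PODCI) score as compared to placebo by Week 17, 33, and 49". Protocol Section 2.2.4.2 adds "Within subject change from baseline in the PODCI through Week 97". Results are to be shown as a Global Function score and five domains. Both documents class the endpoint as exploratory, and PODCI is the only measure named for the functional health status objective.

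Handling: SAP Section 5.3 refers missing PODCI data to the developers' guidance. SAP Section 5.2 lists age among covariates that may be explored. SAP Section 6.3 summarises exploratory endpoints by treatment group and period. Neither document supplies a form for older boys, a rule for a boy who turns 11 on study, an age limit on the PODCI analysis, or a reason for using the 2-10 form above age 10.

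**The concern.** The instrument's stated age range and the enrolled age range do not match in the current text. Followed as written, the plan scores boys of 11 and over on a questionnaire labelled for children up to 10 and pools those scores with in-range ones.

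Two features of the form and its scoring make this more than a label. Many items offer a response for a child who is too young for the activity, which suggests content aimed at younger children. Section 7.11 also allows conversion to normative scores from a large healthy population without saying what ages that population covers.

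The interpretation of the only functional health status measure is at stake. It matters most for the within-subject endpoint through Week 97, where crossing the age limit happens together with time on treatment and no concurrent placebo contrast is planned to separate the two. The 4SC primary analysis, alpha, power and sample size are not touched.

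As background only, the document history records that the 11-18 forms were dropped in Amendment 1 and the upper age was raised in Amendment 2. The point rests on the current text, not on that log.

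**Working it through.** No figure in the plan addresses this, so there is nothing to reproduce. The check compares the age limits and works out when a boy leaves the form's range.

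Inputs:
- Entry age: 6 to <16 years (Section 4.1).
- Form range: up to age 10 (Section 7.11, Appendix 3), read here as before the 11th birthday. This reading is an assumption.
- Assessment days: Week 17 = Day 113, Week 33 = Day 225, Week 49 = Day 337, Week 97 = Day 673 (Schedule of Activities).

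Formula: highest entry age still in range at a visit = 11 − (Day − 1)/365.25.

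| Visit | Years from Day 1 | Entry age at which 11 is reached |
|---|---|---|
| Baseline | 0 | 11.00 |
| Week 17 | 112/365.25 = 0.31 | 10.69 |
| Week 33 | 224/365.25 = 0.61 | 10.39 |
| Week 49 | 336/365.25 = 0.92 | 10.08 |
| Week 97 | 672/365.25 = 1.84 | 9.16 |

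This gives three groups by entry age:
- Below about 9.16: in range at every PODCI.
- About 9.16 to <11: in range at entry, out of range by Week 97.
- 11 to <16: out of range from the first PODCI. The oldest would be just under 16 + 1.84 = 17.84 years at Week 97.

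The documents give no age distribution, so the share of boys affected can only be illustrated, here with entry ages uniform over each interval:
- All enter at 6 to <10: none are out at baseline. None are out at Week 49 either, because the threshold of 10.08 exceeds 10. By Week 97, (10 − 9.16)/(10 − 6) = 21% are out.
- All enter evenly over 6 to <16: (16 − 11)/10 = 50% are out at baseline and (16 − 9.16)/10 = 68% by Week 97.

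The second line describes the eligible age span. It does not estimate the proportion of boys enrolled.

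**The case against.** The best defence is that the planned comparison survives. Every boy is scored on the same form, by a parent or guardian, as change from his own baseline. Through Week 49 the contrast is with randomised placebo, so older boys are expected in both arms. The endpoint is exploratory and carries no alpha and no sample-size role.

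Older boys may also be few. Protocol Section 1.3 puts loss of walking mostly at 10 to 14 years. Entry requires ambulation and a minimum stair-climbing speed. The dose simulations in Section 1.9 assumed ages 6 to 10. The study began in November 2014 (Section 1.7) with 30 months of enrolment foreseen (Section 3.3), and the wider age limit is dated 15 August 2016, about 21 months in.

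Much of this stands. A reader might infer that the arm difference in PODCI cannot be interpreted. The documents do not support that: a common form, within-boy change and randomisation protect the Period 1 contrast, and the plausible loss is sensitivity in older boys. Two qualifications remain. Randomisation is stratified on 4SC time rather than age, so age balance in sequence groups of 35 is expected but not assured. The Week 97 within-subject endpoint also lacks this protection.

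A reader might also infer that half to two thirds of boys are affected. Those are shares of the age span, and the points above suggest fewer. Nor can one conclude that no reference group exists for older boys: Section 7.11 gives no age range for the healthy population, and the SAP plans no normative conversion.

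The defence does not supply a stated reason for using the 2-10 form above age 10, or any rule for handling those scores.

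**Conclusion.** The mismatch is real and lies in the operative text. Assessments at age 11 or older are outside the form's stated range: from the start for boys entering at 11 or over, and later on study for those entering between about 9.2 and 11.

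Its extent among enrolled boys is unknown. Under the younger illustration (6 to <10, uniform) it is 0% at baseline and through Week 49, and about 21% by Week 97. It rises with every boy enrolled above 10. These figures assume the limit is the 11th birthday and that visits fall on nominal days.

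The documents do not show how the form performs above age 10, so neither the size nor the direction of any bias can be computed. The supported conclusion is limited: PODCI scores at 11 or older are not backed by the form's stated range, the randomised Period 1 contrast is weakened for older boys, and within-subject change through Week 97 is the more exposed result. Because PODCI is exploratory, no confirmatory conclusion depends on it.

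**What to change.** In SAP Sections 3.3.3 and 6.3:
- Present the PODCI results (Global Function and five domains) from assessments made before age 11, and show assessments at age 11 or older separately.
- Make no normative conversion for assessments at 11 or older unless the reference population covers that age.

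In Protocol Section 7.11 and Appendix 3, do one of two things:
- Provide an age-appropriate form for newly enrolled boys aged 11 or over, reported separately by form and not pooled with the 2-10 form.
- State the justification for keeping the 2-10 form for all.

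Assigning a form by age at randomisation and keeping it throughout would not be enough alone. A boy entering at 10.9 would still be on the 2-10 form at 10.9 + 1.84 = 12.7 years, so the split by age at assessment is needed either way.

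The SAP change is wording and a tabulation. A second form would also need loading on the tablet already used for PODCI. The cost is a smaller PODCI analysis set, and one that shrinks with follow-up: at Week 97 the in-range set holds only boys who entered before about 9.2 years, so it is also younger than the randomised population.

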## **8. ADVERSE EVENT REPORTING**

### **8.1. Adverse Events**

All observed or volunteered AEs regardless of treatment group or suspected causal relationship to the investigational product(s) will be reported as described in the following sections.

For all AEs, the investigator must pursue and obtain information adequate both to determine the outcome of the AE and to assess whether it meets the criteria for classification as a serious adverse event (SAE) requiring immediate notification to Pfizer or its designated representative. For all AEs, sufficient information should be obtained by the investigator to determine the causality of the AE. The investigator is required to assess causality. Follow-up by the investigator may be required until the event or its sequelae resolve or stabilize at a level acceptable to the investigator, and Pfizer concurs with that assessment.

As part of ongoing safety reviews conducted by the sponsor, any nonserious AE that is determined by the sponsor to be serious will be reported by the sponsor as an SAE. To assist in the determination of case seriousness, further information may be requested from the investigator to provide clarity and understanding of the event in the context of the clinical study.

### **8.2. Reporting Period**

For SAEs, the active reporting period to Pfizer or its designated representative begins from the time that the subject provides informed consent, which is obtained prior to the subject's participation in the study, ie, prior to undergoing any study-related procedure and/or receiving investigational product, through and including 84 calendar days after the last administration of the investigational product. SAEs occurring to a subject after the active reporting period has ended should be reported to the sponsor if the investigator becomes aware of them; at a minimum, all SAEs that the investigator believes have at least a reasonable possibility of being related to investigational product are to be reported to the sponsor.

- AEs (serious and nonserious) should be recorded on the case report form (CRF) from the time the subject has taken at least 1 dose of investigational product through the subject's last visit.

### **8.3. Definition of an Adverse Event**

An AE is any untoward medical occurrence in a clinical investigation subject administered a product or medical device; the event need not necessarily have a causal relationship with the treatment or usage. Examples of AEs include but are not limited to:

- Abnormal test findings;
- Clinically significant symptoms and signs;
- Changes in physical examination findings;
- Hypersensitivity;
- Progression/worsening of underlying disease
- Drug abuse;
- Drug dependency.

Additionally, they may include the signs or symptoms resulting from:

- Drug overdose;
- Drug withdrawal;
- Drug misuse;
- Drug interactions;
- Extravasation;
- Exposure during pregnancy (EDP);
- Exposure via breastfeeding;
- Medication error;
- Occupational exposure.

### **8.4. Medication Errors**

Medication errors may result, in this study, from the administration or consumption of the wrong product, by the wrong subject, at the wrong time, or at the wrong dosage strength.

Such medication errors occurring to a study participant are to be captured on the medication error CRF which is a specific version of the AE page, and on the SAE form when appropriate. In the event of medication dosing error, the sponsor should be notified immediately.

Medication errors are reportable irrespective of the presence of an associated AE/SAE, including:

- Medication errors involving subject exposure to the investigational product;
- Potential medication errors or uses outside of what is foreseen in the protocol that do or do not involve the participating subject.

Whether or not the medication error is accompanied by an AE, as determined by the investigator, the medication error is captured on the medication error version of the AE page and, if applicable, any associated AE(s) are captured on an AE CRF page.

